10.3 Disease-Free Survival

From date of surgery to date of first documentation of relapse/recurrence or death due to any cause. Patients last known to be alive without report of relapse/recurrence are censored at date of last contact.

10.4 Overall Survival

From date of randomization to date of death due to any cause. Patients last known to be alive are censored at their last contact date.

10.5 Performance Status

Patients will be graded according to the Zubrod Performance Status Scale.

POINT	DESCRIPTION
0	Fully active, able to carry on all pre-disease performance without restriction.
1	Restricted in physically strenuous activity but ambulatory and able to carry out work of a light or sedentary nature, e.g., light housework, office work.
2	Ambulatory and capable of self-care but unable to carry out any work activities; up and about more than 50% of waking hours.
3	Capable of limited self-care, confined to bed or chair more than 50% of waking hours.
4	Completely disabled; cannot carry on any self-care; totally confined to bed or chair.

11.0 STATISTICAL CONSIDERATIONS

11.1 Primary Analysis

The primary objective is to compare, by arm, the proportion of patients who experience any complication (Clavien-Dindo grades I–V) by day 30 after surgery. Prior evidence suggests that approximately 65% of patients will experience complications by Day 30. (120, 121, 122, 123) The design stipulates that a 35% relative reduction in the complication rate due to the intervention would be clinically meaningful, representing a reduction in the complication rate from 65% down to 42% (a 23% absolute reduction). The design also anticipates a 5% non-adherence rate (which reduces the nominal effect size). Based on a two-arm binomial design with continuity correction, a one-sided alpha = 0.05 test and 80% power, a total of 146 eligible, randomized patients will be needed. In addition, in this population, it is anticipated that 20% of patients will drop out after surgery by Day 30, and a small portion of patients (3%) will drop out prior to surgery. Incorporation of this dropout rate inflates the required sample size by a factor of $146/0.77 = 190$ eligible patients. Finally, assuming a 5% ineligibility rate, a total of 200 registered patients will be required. The high-grade complication rate (Clavien Dindo scheme III–V) will also be examined. If the control arm high grade complication rate is 20%, 200 patients will give $\geq 80\%$ power to detect an absolute reduction of 15% (down to 5%).

The primary analysis will be based on a multivariable logistic regression under intent-to-treat among all randomized patients, irrespective of their eligibility status, adjusting for the specified stratification factors: a. Diversion type (neobladder vs. ileal conduit); b. Prior neoadjuvant chemotherapy (any vs. none); and c. Nutrition status (well-nourished vs. moderate malnutrition). A Fisher's exact test will also be conducted to establish whether the results are sensitive to model assumptions. A single interim analysis for efficacy will be conducted when 50% of patients achieve their endpoint at the alpha=0.005 level. Accordingly, the final analysis will be conducted at the alpha=0.045 level. A separate analysis among all eligible randomized patients will also be conducted.

To minimize missed assessments, SWOG utilizes an electronic system to remind institutions in real-time that patients are due for follow-up assessment. Nonetheless missing data will occur. To bracket the final result, Lachin's worst rank analysis will be used by imputing the missing data in the following manner: 1) all missing observations will be assigned the worst rank; 2) all missing observations will be assigned the best rank; 3) all missing observations in the experimental arm will be assigned the worst rank, and all missing observations in the control arm will be assigned the best rank; and 4) all missing observations in the experimental arm will be assigned the best rank, and all missing observation in the control arm will be assigned the worst rank. Finally, using delta adjustment, we will examine how biased the imputation will need to be to substantively influence statistical significance (i.e. turn from statistically significant to not statistically significant) at any given alpha level. (124) In particular, the "truth" will be bracketed by analysis 3 and 4, above. Interpretation will be influenced by the amount of missing data and the magnitude of potential differences between the observed and best/worst-case findings, suggesting uncertainty in the primary result due to missing data.

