10.0 CRITERIA FOR EVALUATION AND ENDPOINT ANALYSIS

10.1 Measurement of Complications

a. **Primary Endpoint: Post-operative Complications** A post-operative complication is defined as a binary indicator variable indicating whether the patient experienced any complication (any/none; Clavien-Dindo grades I-V; Table 1). (118)

Table 1. Clavien-Dindo Scheme

Clavien-Dindo Grades	Definition
Grade I	Any deviation from the normal postoperative course without the need for pharmacological treatment or surgical, endoscopic or radiological interventions. Allowed therapeutic regimens are drugs as antiemetic, antipyretics, analgesics diuretics, electrolytes, and physiotherapy.
Grade II	Requiring pharmacological treatment with drugs other than such allowed for grade I complications. Blood transfusions and total parenteral nutrition are also included.
Grade III	Requiring surgical, endoscopic or radiological intervention
Grade IIIa	Intervention not under general anesthesia
Grade IIIb	Intervention under general anesthesia
Grade IV	Life-threatening complications (including central nervous system complications) requiring intermediate care or intensive care unit management
Grade IVa	Single-organ dysfunction (including dialysis)
Grade IVb	Multi-organ dysfunction
Grade V	Death of a patient
Suffix “d”	If the patient suffers from a complication at the time of discharge, the suffix “d” (for “disability”) is added to the respective grade of complication. This label indicated the need for a follow up to fully evaluate the complication.

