Tertiary objectives include comparing the impact of consuming SIM compared to ONS for restraining MDSCs, decreasing inflammation, and modulating nutrient metabolism. To limit the influence of outliers and aid interpretation across a panel of markers, the marker level results will be log normal-standardized and split at the median level, creating an indicator variable (high vs. low levels of each marker). Assuming complete information, the accrual goal of $n = 200$ total patients will provide adequate power ($>80\%$) to detect a $>20\%$ change in the proportion of patients with high or low marker levels due to SIM, based on a two-arm normal design, one-sided alpha = 0.05 testing, and assuming the average rate of high or low marker levels across arms of 50%.

In addition, we will examine whether these biomarkers influence the association between intervention and the clinical outcomes. As a more exploratory analysis, we will use a two-sided nominal P -value = 0.10 to identify potentially significant interactions. (18) Under a binomial interaction design, equal sample sizes in each cell, a one-sided alpha = 0.10, and a 65% event probability for the ONS arm, $n = 200$ patients will give adequate power ($\geq 80\%$) to detect a 3.8-fold increased odds of complications on the ONS arm in stratum 1 (i.e., high-expression group) if there is no effect in stratum 2 (i.e., low-expression group). In the case of a significant interaction indicating differential complication rates by arm between marker categories, further specific analyses will be performed to identify the actual differences. It is recognized that these results will not be definitive due to the limited power and multiple testing problem, although hypotheses will be based on biologic rationale. Promising observations will need to be validated in future data sets due to the exploratory nature of this component of the study.

We will also explore whether dietary intake variables, derived from data obtained from the dietary intake telephone interview, influence the association between intervention and outcome. The specific variables of interest include calorie intake, protein intake, nutrition status, and immune-enhancing nutrients.

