This translational study to examine changes in the gut microbiome with intervention is being incorporated into the currently activated and enrolling SWOG **S1600** trial. Patients' stool samples will be collected with the Omniprene-GUT kit. This kit allows the patient to collect and preserve the samples from the comfort of their own home. Patients will be asked to collect a stool specimen and place a small sample on the kit spatula. This is then placed into the tube provided. With the Omniprene-GUT kit the yield of DNA is not influenced by temperature, thus it should be able to be shipped at any time of the year in any climate. (21) Once the samples have been collected they are stable in the test tube for 60 days at room temperature. Collection timepoints and instructions are located in [Section 15.2](#). They will begin their nutritional supplements 5 days before surgery and then undergo surgery per the **S1600** protocol. As the **S1600** protocol dictates strict timing of drink delivery, the first specimen can be collected anytime after **S1600** enrollment, but before initiation of their first nutritional drink (control or immunonutrition). After discharge from the hospital, we will have them collect the first bowel movement that occurs at home (+/- 2 days). Although waiting until after discharge means the timing of collection of the post-surgical sample will vary based on each patient's duration of hospitalization, collection of the sample during hospitalization at each participating institution is anticipated to be logistically

difficult and therefore unreliable. These kits have been used in [name] lab previously for other studies that require shipping the specimens internationally, and extraction of these shipped samples has yielded the same results as fresh samples collected locally in the lab. (22) SWOG Biospecimen Bank will process specimens per the Omniprene-GUT website. The samples will be stored in -80 degree freezer until end of study. Frozen samples will be shipped from SWOG Biospecimen Bank to the University of Colorado for analysis. DNA will be extracted and sequenced using standard 16s rRNA technique, using the DNeasy PowerSoil kit from Qiagen using the manufacturer's instructions, with the addition of a 65 degree incubation step and homogenization with bead-beating rather than vortex. (23) The bead-beating will facilitate release of DNA from gram positive bacteria.

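### Does the interim split of 0.005 and 0.045 undermine the 146 patients and 80% power that were derived for a single one-sided 0.05 test?

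*Combined protocol and SAP*

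**What the plan says.** Section 11.1 of the combined protocol and SAP assumes a 30-day complication rate of 65% on control and 42% on the immune-modulating drink, with 5% non-adherence reducing the effect. It uses a continuity-corrected two-arm binomial design: "a one-sided alpha = 0.05 test and 80% power, a total of 146 eligible, randomized patients will be needed". Dropout of 23% takes this to 190, and 5% ineligibility takes it to 200 registered.

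The next paragraph describes the analysis. The primary model is a logistic regression "among all randomized patients, irrespective of their eligibility status", and the eligible-only set is a separate analysis. On monitoring it says: "A single interim analysis for efficacy will be conducted when 50% of patients achieve their endpoint at the alpha=0.005 level", and then "Accordingly, the final analysis will be conducted at the alpha=0.045 level".

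Section 10.1 defines the endpoint: "A post-operative complication is defined as a binary indicator variable indicating whether the patient experienced any complication".

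**The concern.** Three things look wrong together.

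- **Sizing and testing differ.** The 146 and the 80% belong to one test at 0.05, but the final test is run at 0.045. A reader cannot match the stated power to the boundary in use, and might suspect either that error is overspent or that power has been lost.
- **The levels carry no side.** If 0.005 and 0.045 were two-sided, the trial would spend only 0.0235 in the direction of benefit and power would be about 69% at 146. Appendix 18.2 adds to the doubt. For its exploratory interaction test it first says "we will use a two-sided nominal" level of 0.10, and then bases the power on "equal sample sizes in each cell, a one-sided alpha = 0.10".
- **The trigger is ambiguous.** For a yes/no endpoint, achieving the endpoint could mean reaching the Day-30 assessment or having a complication, and the denominator is not given.

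At stake would be whether a final one-sided p-value just above 0.045 counts as positive, whether the design has its claimed power, and when the only efficacy look takes place.

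**Working it through.** **Inputs.** Section 11.1 gives p1 = 0.65, p2 = 0.42, 5% non-adherence, one-sided 0.05, 80% power, continuity correction, 23% dropout and 5% ineligibility. Equal allocation (73 per arm) comes from Section 18.9. Two assumptions are needed: non-adherence dilutes the experimental arm only, so p2 = 0.42 + 0.05 × 0.23 = 0.4315, and the interim falls at half information.

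**Step 1: reproduce 146.** Here d = 0.65 − 0.4315 = 0.2185 and p̄ = 0.54075, so 2p̄(1−p̄) = 0.4967 and p1(1−p1) + p2(1−p2) = 0.4728.

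- Uncorrected, per arm: m = (1.645√0.4967 + 0.8416√0.4728)² / 0.2185² = 63.26.
- Corrected: n = (m/4)(1 + √(1 + 4/(m·d)))² = 72.13, so 73 per arm and **146**, the stated figure.
- The rest follows: 146/0.77 = 189.6, rounded to 190, and 190/0.95 = 200.

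The same formula at one-sided 0.045 gives m = 65.88 and n = 74.76, so 75 per arm, or 150. The sizing therefore does leave out the interim look, at a cost of four evaluable patients.

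**Step 2: type I error.** The sum 0.005 + 0.045 = 0.05 is an upper bound at any interim timing. The exact large-sample value is 1 − Φ₂(2.576, 1.695; √t), where Φ₂ is the bivariate normal distribution function with correlation √t:

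| Information fraction t | Total one-sided error |
|---|---|
| 0.30 | 0.0478 |
| 0.40 | 0.0472 |
| 0.50 | 0.0466 |
| 0.60 | 0.0460 |
| 0.70 | 0.0456 |

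The split is valid and slightly conservative.

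**Step 3: power over both looks.** Power = 1 − Φ₂(2.576 − θ√t, 1.695 − θ; √t) at t = 0.5, where θ = 1.645 + z(power of the single 0.05 test). At 146 with the correction, single-test power is 80.5% and θ = 2.504. The all-randomized set is expected to hold 200 × 0.77 = 154 evaluable patients.

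| Evaluable | Continuity correction | Single test at 0.05 | Looks at 0.005 and 0.045 |
|---|---|---|---|
| 146 | yes | 80.5% | 79.3% |
| 154 | yes | 82.6% | 81.4% |
| 146 | no | 84.8% | 83.8% |
| 154 | no | 86.5% | 85.5% |

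Only the first row falls below 80%. It pairs the eligible-only count with a correction that the logistic model does not use.

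**Step 4: would a larger final level help?** At t = 0.5, the final level that spends exactly 0.05 is 0.0485. With the correction, power rises from 79.3% to 80.2% at 146 and from 81.4% to 82.3% at 154. Because the outcome is binary, the actual error differs from the large-sample value. Simulating the unadjusted score test with 65% in both arms (400,000 runs) gave 0.048 at 146 and 0.047 at 154 with 0.045, against 0.051 and 0.053 with 0.0485. Repeat runs stayed within 0.046 to 0.049 and 0.051 to 0.053 respectively.

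**Step 5: the two wording gaps.**

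- *Side.* Section 11.1 fixes a one-sided 0.05, takes 0.005 from it, and introduces 0.045 as what follows. The levels sum to that 0.05. Appendix 18.2 also uses one-sided 0.05 for its main marker comparison.
- *Trigger.* If it meant complications equal to half of 146, 73 events at a mean rate of 54% would need 73/0.54 ≈ 135 of the 146 patients. If it meant half of 200, 100 events would be needed, but at the 53% overall rate in Section 18.9 only 154 × 0.53 ≈ 82 are expected. Half the patients having reached Day 30 is the only reading that works as an interim.

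**The case for a change.** The best argument for a change is not the one point of power but the missing words. Without a stated side, a final one-sided p-value of 0.03 is positive on one reading and negative on the other, since a two-sided 0.045 puts 0.0225 in each tail. Power on the two-sided reading is 69.4% at 146 and 72.0% at 154. The interim timing is likewise left to inference, and Appendix 18.2 shows that the document is not consistent about sides. One sentence would settle both, at no cost in patients.

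Part of this stands: neither level is labelled, and no denominator is given for the trigger. But the two-sided reading conflicts with the section's own logic, and the contrary evidence comes from an exploratory analysis in another part of the document. The trigger cannot affect validity, because the two levels sum to 0.05 at any timing. An analyst following Section 11.1 would apply one-sided levels and look when half the patients have Day-30 status, so the clarification would change no result.

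It can also be said that 0.045 gives away alpha: a final one-sided p-value between 0.045 and about 0.0485 would be called negative although the nominal 5% would still be kept. That holds in large samples. At this trial's size the simulation suggests the margin is largely used up by the discreteness of the outcome.

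**Conclusion.** The observation is correct, but it does not call for a change. The sizing ignores the interim look, which costs about one point of power: 79.3% instead of 80.5% at 146 with the continuity correction. The planned primary analysis has about 81% with the correction and about 85% without it at the expected 154, so the stated 80% is met. The type I error is bounded by 0.05 at any interim timing and is 0.0466 at half information.

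A fixed 0.045 that needs no known information fraction is a fair trade-off against a recomputed level. The alternative gains about one nominal point of power and gave simulated error of 0.051 to 0.053. It would also mean amending the boundary of a trial that Section 18.9 describes as already under way (the stool study "is being incorporated into the currently activated and enrolling" trial). Labelling the levels one-sided and giving the trigger as a count of patients with known Day-30 status would be tidy but is optional.

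This rests on one-sided levels, dilution of the experimental arm only, equal allocation, an interim near half information, and the planned 23% dropout applying to all 200 randomized. The simulated error rates are for an unadjusted score test, not the covariate-adjusted logistic model.

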11.2 Secondary Analysis

A set of secondary objectives will also be examined. Additional factors that are potentially prognostic for complication rates will be examined as covariates in separate logistic regression analyses, to assess the sensitivity of the primary logistic regression model

results to additional covariate adjustment; factors include BMI (< 30 vs. \geq 30), age (< 65 vs. \geq 65 years), gender (male vs. female), diabetes mellitus, pathologic staging, pro-inflammatory cytokines known to affect appetite, background diet, current use of supplements, and any autoimmune disease. Also, in addition to the primary endpoint assessment of any complication at Day 30, we will assess the complication rate at day 90, as well as a composite endpoint with three levels (complications by Day 30, complication after Day 30 but by Day 90, and no complications by Day 90). In addition, we will examine the impact of SIM use on the Day 30 and Day 90 rates of infection (as determined by antibiotic use outside of prophylaxis), skeletal muscle mass, high-grade post-operative complications (Clavien Dindo Grades III–V), and readmission rates. To consider whether dropout may be non-random (i.e., informative), which could influence the results, a sensitivity analysis will be conducted that counts dropouts as events. Although death rates are anticipated to be low, 2-year overall survival by arm will be explored using Kaplan Meier curves, as will disease-free survival. The relationship between compliance and outcomes will be explored. A set of tertiary objectives will also be examined as indicated in [Appendix 18.2](#).

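### Does Section 11.1 need a rule for patients who drop out with a complication already on record?

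*Combined protocol and SAP*

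**What the plan says.** Section 10.1a makes the primary endpoint a binary variable "indicating whether the patient experienced any complication", Clavien-Dindo grade I to V. Objective 1.1 and Section 11.1 set the limit at 30 days after surgery.

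Section 11.1 plans a logistic regression under "intent-to-treat among all randomized patients, irrespective of their eligibility status". For missing outcomes it lists four imputations: all worst, all best, and the two opposed assignments. In analysis 3, "all missing observations in the experimental arm will be assigned the worst rank" and the control arm gets the best rank; analysis 4 is the mirror image. The truth, it says, "will be bracketed by analysis 3 and 4, above". A delta adjustment then asks how biased the imputation must be before significance changes.

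On sample size, Section 11.1 states that "it is anticipated that 20% of patients will drop out after surgery by Day 30". It expects another 3% to leave before their operation, and so divides the 146 patients needed by 0.77 to reach 190. Section 11.2 adds that "a sensitivity analysis will be conducted that counts dropouts as events".

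Sections 7.10 and 14.1 require forms and data for all registered patients, including those who come off protocol early. No section defines a missing observation.

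**The concern.** With 23% drop-out planned, how drop-outs are coded is not an edge case. Two readings seem open. On the first, every drop-out is missing: the divisor 0.77 plans for no outcome from any of them, and the one scheduled Clavien-Dindo assessment by Day 30 is the Day-30 visit. On the second, a complication recorded before the patient leaves counts as an observed event, and only drop-outs with nothing on record are missing.

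The choice matters most in analysis 3. SIM drop-outs count as events there on either reading, whereas a control drop-out with a recorded complication moves from non-event to event. The worst-case estimate can therefore change direction on the same data. If the coding were chosen after unblinding, it could decide whether the worst case still leans towards SIM. On the second reading the missing share also differs by arm, and leaving event-free drop-outs out of the regression raises both observed rates.

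**Working it through.** **Inputs from Section 11.1.** Control rate 65%; SIM rate 42%; 5% non-adherence; one-sided alpha 0.05; 80% power; continuity correction; drop-out 20% after surgery and 3% before.

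**Inputs assumed.** Drop-outs have the same complication risk as completers in their arm. A share d of post-surgery drop-outs' complications is on record when they leave. The documents give no value for d, so the range is 0 to 1; d = 0 is the same as treating every drop-out as missing.

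**The plan's own figures.** Diluted SIM rate: 0.65 − 0.95 × 0.23 = 0.4315. Two proportions, 0.65 against 0.4315, with continuity correction: 72.1, rounded up to 73 per arm, or 146 in total. Then 146/0.77 = 190 and 190/0.95 = 200. All three totals reproduce.

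**Formulas, for an arm with rate p.**
- Observed events: 0.77p + 0.20pd
- Missing: 0.03 + 0.20(1 − pd)
- Analysis 3, SIM: 0.77 × 0.4315 + 0.23 = 0.5623 for any d
- Analysis 3, control: 0.77 × 0.65 + 0.20 × 0.65d = 0.5005 + 0.13d
- Analysis 4, SIM: 0.3323 + 0.0863d
- Analysis 4, control: 0.5005 + 0.23 = 0.7305 for any d

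| d | Missing, control / SIM | Analysis 3, control minus SIM | Analysis 4, control minus SIM |
|---|---|---|---|
| 0 | 23.0% / 23.0% | −6.2 points | +39.8 points |
| 0.5 | 16.5% / 18.7% | +0.3 | +35.5 |
| 1 | 10.0% / 14.4% | +6.8 | +31.2 |

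A positive difference favours SIM. Analysis 3 crosses zero at d = 0.0618/0.13 = 0.475, when 0.0618/0.20 = 30.9% of control post-surgery drop-outs have a complication on record. With 42% in place of 43.15%, it runs from −5.3 to +7.7.

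**Effect on the inference.** Expected counts at 95 per arm, one-sided Fisher test for benefit:

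| d | Analysis 3 events, SIM / control | p | Analysis 4 events, SIM / control | p |
|---|---|---|---|---|
| 0 | 53 / 48 | 0.81 | 32 / 69 | <0.0001 |
| 0.5 | 53 / 54 | 0.50 | 36 / 69 | <0.0001 |
| 1 | 53 / 60 | 0.19 | 40 / 69 | <0.0001 |

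Against the final level of 0.045, the conclusion is the same in every row: the result does not survive the worst case and does survive the best case.

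**Effect on the primary test.** If missing patients are left out, observed events are p(0.77 + 0.20d) and observed non-events 0.77(1 − p). The factor (0.77 + 0.20d)/0.77 multiplies the odds in both arms and cancels, so the odds ratio is (0.4315/0.5685)/(0.65/0.35) = 0.41 for every d. The observed rates do rise, from 65.0% and 43.2% at d = 0 to 70.1% and 48.9% at d = 1.

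**Do the passages really conflict?** A recorded complication by Day 30 makes the Section 10.1a variable positive, and nothing later can undo that, so there is nothing left to impute. The 0.77 divisor is an allowance for planning, not a coding rule. The Section 11.2 analysis counts a drop-out with a recorded complication as an event on either reading, so it favours neither.

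**The case for a change.** The best case for a change is that Section 11.1 ties interpretation to the amount of missing data and to the gap between observed and extreme-case results, and both depend on the missing definition. From d = 0 to d = 1 the bracket narrows from 46.0 points (39.8 + 6.2) to 24.4 (31.2 − 6.8). In simulation at 95 per arm with 42% in the SIM arm, the two codings gave opposite signs in analysis 3 in about 28% of trials at d = 0.5 and 59% at d = 1. A rule costs a sentence or two, and a supportive Kaplan-Meier estimate to Day 30 would deal with event-free drop-outs.

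Some of this stands. The definition is unwritten, the bracket width does depend on it, and writing it down before unblinding would do no harm. But the sign change is in a point estimate that is non-significant on both codings. It also requires the planned 20% to include patients whose outcome is already known. If that 20% means patients with no usable outcome, which is how the divisor uses it, then d is 0 by definition and nothing reverses. The Kaplan-Meier estimate alters no stated test, assumes drop-out is unrelated to later complications, and needs onset and last-contact dates that the documents do not show are collected. It also leaves unsaid how event-free drop-outs enter the regression.

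**Conclusion.** No change follows. This is a gap in wording that analysts would fill the same sensible way: a complication recorded by Day 30 is an event, while drop-outs with none on record and patients never operated on are missing. Analysis 3 can move from 6.2 points for control to 6.8 points for SIM, but only across the full range of an assumed recording share, with equal risk in drop-outs and completers, and with recorded complications counted inside the 20% allowance. The primary odds ratio stays at 0.41 if complications are recorded equally well in the two blinded arms, analysis 4 never changes sign, and analysis 3 is non-significant at expected counts on either coding. A definition and by-arm counts of drop-outs with and without a recorded complication would be good reporting practice, but the plan is not in error without them.
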